3.3.4 Withdrawal of subjects from treatment or assessments

Subjects may withdraw or may be removed from trial treatment or may withdraw consent to trial participation as a whole ('withdrawal of consent') with very different implications; please see Sections 3.3.4.1 and [3.3.4.2](#) below.

If a subject is removed from or withdraws from the trial prior to the first administration of trial medication, the data of this subject will not be entered in the case report form (CRF) and will not be reported in the clinical trial report (CTR).

If a subject is removed from or withdraws from the trial after the first administration of trial medication, this will be documented and the reason for discontinuation must be recorded in the CRF; in addition, trial data will be included in the CRF and will be reported in the CTR.

Following removal or withdrawal, a complete end-of-trial examination should be performed. If the discontinuation or withdrawal occurs before the end of the REP (see Section [1.2.2](#), the discontinued subject should, if possible, be questioned for AEs and concomitant therapies at or after the end of the REP, in order to ensure collection of AEs and concomitant therapies throughout the REP, if not contrary to any consent withdrawal of the subject.

3.3.4.1 Withdrawal from trial treatment

An individual subject will be withdrawn from trial treatment if:

1. The subject wants to withdraw from trial treatment. The subject will be asked to explain the reasons but has the right to refuse to answer
2. The subject has repeatedly shown to be non-compliant with important trial procedures and, in the opinion of both, the investigator and sponsor representative, the safety of the subject cannot be guaranteed as he / she is not willing or able to adhere to the trial requirements in the future.
3. The subject needs to take concomitant medication that interferes with the investigational medicinal product or other trial treatment
4. The subject can no longer receive trial treatment for medical reasons (such as pregnancy, surgery, adverse events (AEs), or diseases). Specifically the subject will not receive further trial treatment if he/she experiences a severe adverse drug reaction (i.e. a severe adverse event judged to be related to trial medication).
5. The subject has an elevation of AST and/or ALT ≥ 3 -fold ULN and an elevation of total bilirubin ≥ 2 -fold ULN (measured in the same blood sample) and/or needs to be followed up according to the DILI checklist provided in the electronic data capture (EDC) system.
6. The subject exhibits serious suicidality, in the clinical judgment of the investigator or according to the following criteria:
 - Any suicidal behaviour (i.e. actual attempt, interrupted attempt, aborted attempt, or preparatory acts or behaviour)

Proprietary confidential information © 2022 Boehringer Ingelheim International GmbH or one or more of its affiliated companies

- Any suicidal ideation of type 2, 3, 4 or 5 in the C-SSRS (i.e. active suicidal thought without method, intent or plan; active suicidal thought with method but without intent or plan; active suicidal thought with method and intent but without specific plan; or active suicidal thought with method, plan and intent)

In addition to these criteria, the investigator may discontinue subjects at any time based on his or her clinical judgment.

If it is known that a subject becomes pregnant during the trial, administration of the trial medication is to be stopped immediately, and the subject is to be removed from the trial. The subject is to be followed until she has given birth or until the end of the pregnancy. The subject's data are to be collected until the end of the trial (last visit of last subject) and reported in the CTR. For reporting of pregnancy and associated events, refer to Section [5.2.6.2.3](#).

If new efficacy or safety information becomes available, Boehringer Ingelheim will review the benefit-risk-assessment and, if needed, pause or discontinue the trial treatment for all subjects or take any other appropriate action to guarantee the safety of the trial subjects.

3.3.4.2 Withdrawal of consent to trial participation

Subjects may withdraw their consent to trial participation at any time without the need to justify the decision. If a subject wants to withdraw consent, the investigator should be involved in the discussion with the subject and explain the difference between trial treatment discontinuation and withdrawal of consent to trial participation, as well as explain the options for continued follow-up after trial treatment discontinuation, please see Section [3.3.4.1](#) above.

3.3.4.3 Discontinuation of the trial by the sponsor

Boehringer Ingelheim reserves the right to discontinue the trial at any time for any of the following reasons (if reasons 4 and/or 5 are met, the trial should be discontinued immediately):

1. Failure to meet expected enrolment goals overall or at a particular trial site
2. The sponsor decides to discontinue the further development of the investigational products
3. Deviation from GCP, or the CTP impairing the appropriate conduct of the trial
4. New toxicological findings, serious adverse events, or any safety information invalidating the earlier positive benefit-risk-assessment (see Section 3.3.4.1)
5. More than 50% of the subjects show drug-related and clinically relevant adverse events of moderate or severe intensity, or if at least one drug-related serious adverse event is reported

The trial will be at least temporarily halted if two or more severe adverse reactions (i.e. severe adverse events judged to be related to trial medication) are reported.

3.3.5 Replacement of subjects

In case more than 4 subjects do not complete the trial (including subjects non- evaluable for PK), subjects may be replaced if considered necessary to reach the objective of the trial. Subjects who withdraw or are withdrawn from treatment or assessments because of a drug-related adverse event will not be replaced. The Clinical Trial Leader together with the Trial Pharmacokineticist and the Trial Statistician are to decide, if and how many subjects will be replaced. The total number of replacements may not exceed 1/3 of the total number of evaluable subjects anticipated to complete the trial. A replacement subject will be assigned a unique trial subject number, and will be assigned to the same treatment sequence as the subject he or she replaces.

4. TREATMENTS

4.1 INVESTIGATIONAL TREATMENTS

4.1.1 Identity of the Investigational Medicinal Products

The characteristics of the test product (T) are given below:

Substance: BI 1358894

Pharmaceutical formulation: film-coated tablet, iCF

Source: BI Pharma GmbH & Co. KG, Germany

Unit strength: 100 mg

Posology: 1-0-0

Mode of administration: Oral

The characteristics of the reference product (R) are given below:

Substance: BI 1358894

Pharmaceutical formulation: film-coated tablet, TFII (conventional form: C1)

Source: BI Pharma GmbH & Co. KG, Germany

Unit strength: 50 mg

Posology: 2-0-0

Mode of administration: Oral

4.1.2 Selection of doses in the trial

The dose selected for this trial is one of the standard clinical doses (see Section [1.2](#)).

4.1.3 Method of assigning subjects to treatment groups

The randomisation scheme will be provided to the trial site in advance.

Subjects will be allocated to treatment sequences prior to the first administration of trial medication in the morning of Day 1 (Visit 2). For this purpose, numbers of the randomisation

scheme will be allocated to the subjects by drawing lots. Subjects are then assigned to a treatment sequence according to the randomisation scheme. Once a subject number has been assigned, it cannot be reassigned to any other subject. All subjects may be treated in one cohort, i.e. all subjects may receive treatment on the same calendar day. In case this is not feasible (e.g., due to logistical or recruitment reasons), the group may be split into several cohorts as required. Treatment of all subjects on the same calendar day is acceptable based on the data available for BI 1358894. For discussion of trial-associated risks and safety measures, see Section [1.4](#)).

The randomisation procedure is described in Section [7.4](#).

4.1.4 Drug assignment and administration of doses for each subject

This is a 4-way crossover trial. All subjects will receive the 4 treatments in randomised order. The treatments to be evaluated are summarised in Table 4.1.4: 1 below.

Table 4.1.4: 1 Dosage and treatment schedule

Treatment	Substance	Formulation	Unit strength	Dosage	Metabolic state	Total dose
T _{fasted}	BI 1358894	iCF	100 mg	1 film-coated tablet qd	Fasted	100 mg
T _{fed}	BI 1358894	iCF	100 mg	1 film-coated tablet qd	Fed	100 mg
R _{fasted}	BI 1358894	TFII	50 mg	2 film-coated tablets qd	Fasted	100 mg
R _{fed}	BI 1358894	TFII	50 mg	2 film-coated tablets qd	Fed	100 mg

Administration of trial medication in two treatment periods (treatments T_{fasted} and R_{fasted}) will be performed after subjects have fasted overnight; fasting is to start no later than 10 h before the scheduled dosing. The investigator (or authorised designee) will administer the trial medication as an oral dose together with about 240 mL of water to subjects who are in a standing position. For drug administration, the so-called four-eye principle (two-person rule) should be applied. For this, one authorised employee of the trial site should witness the administration of trial medication, and – if applicable – its preparation, if correct dosage cannot be ensured otherwise. In two treatment periods (treatments T_{fed} and R_{fed}), the subjects will start to consume a high-fat, high-calorie meal 30 min before drug administration. The subjects must completely consume the meal prior to drug intake. The composition of the standard high-fat, high-calorie meal is detailed in Table [4.1.4: 2](#); this meal is in compliance with the FDA guidance ‘Food-Effect Bioavailability and Fed Bioequivalence Studies’ [[R03-2269](#)]. For restrictions with regard to diet, see Section [4.2.2.2](#).

Proprietary confidential information © 2022 Boehringer Ingelheim International GmbH or one or more of its affiliated companies

Table 4.1.4: 2

Composition of the high-fat, high-calorie meal

Ingredients	kcal
2 chicken eggs (whole content) for scrambled eggs	192
10 g butter for frying scrambled eggs	75
35 g fried bacon	186
2 toasted slices of wheat bread	130
15 g butter for buttering toast slices	113
115 g hash brown potatoes	132
240 mL whole milk (3.5% fat)	156
Sum¹	984

¹ The total caloric content was supplied approximately as following: 150 kcal as protein, 250 kcal as carbohydrate, and 500 to 600 kcal as fat.

Subjects will be kept under close medical surveillance until 24 h after drug administration. During the first 4 h after drug administration, subjects are not allowed to lie down (i.e. no declination of the upper body of more than 45 degrees from upright posture).

The treatments will be separated by a wash-out phase of at least 17 days.

4.1.5 Blinding and procedures for unblinding

The table below summarizes the masking/blinding level of individual functions, roles and responsibilities involved in the trial.

Table 4.1.5: 1

Blinding level of individual functions

Role/function	Timing of receiving access to the treatment information (including rationale)
Subject/Participant	This open label trial will provide the subject treatment information as soon as treatment has been assigned.
Investigator/Site Staff	The randomization scheme will be provided to the trial site prior to first subject entered for preparation of medication.
Sponsor trial team and data	Unblinded as requested.
Bioanalytical Staff	Persons directly involved in bioanalyses of PK samples will be blinded to trial treatments.
Pharmacokineticist/ Pharmacometrist	As requested for analysis.
Unblinded Pharmacist/ Pharmacy staff	Prior to first subject entered.

During the time a role/function is blinded according to the table above, the randomisation schemes (i.e. the treatment information) are kept restricted by the global Randomization Team per Sponsor SOP.

Proprietary confidential information © 2022 Boehringer Ingelheim International GmbH or one or more of its affiliated companies

PK samples will be labelled in such a way that treatment allocation cannot be derived by the analytical site.

4.1.6 Packaging, labelling, and re-supply

The investigational medicinal products will be provided by BI. They will be packaged and labelled in accordance with the principles of Good Manufacturing Practice (GMP).

For details of packing and the description of the label, refer to the ISF.

The telephone number of the sponsor and the name address and telephone number of the trial site are provided in the subject information form. The EudraCT number is indicated on the title page of this protocol as well as on the subject information and informed consent forms.

Packaging and labelling will be performed in such a way that reserve samples as per 21CFR320 are available for storage by the investigational site and that the trial materials can be chosen in a random way by the Investigator.

No re-supply is planned.

4.1.7 Storage conditions

Drug supplies will be kept in their original packaging and in a secure limited access storage area in accordance with the recommended (labelled) storage conditions. If necessary, a temperature log must be maintained to make certain that the drug supplies are stored at the correct temperature. If the storage conditions are found to be outside the specified range, the Clinical Research Associate (as provided in the list of contacts) is to be contacted immediately.

4.1.8 Drug accountability

The investigator or designee will receive the investigational drugs delivered from the sponsor when the following requirements are fulfilled:

- Approval of the clinical trial protocol by the IRB / ethics committee
- Approval/notification of the regulatory authority, e.g. competent authority
- Availability of the *curriculum vitae* of the Principal Investigator
- Availability of a signed and dated clinical trial protocol

Only authorised personnel documented in the form 'Trial Staff List' may dispense investigational drugs to trial subjects. Investigational drugs are not allowed to be used outside of this protocol.

The investigator or designee must maintain records of the product's delivery to the trial site, the inventory at the site, the use by each subject, and the disposal of unused products. These records will include dates, quantities, batch / serial numbers, expiry ('use-by') dates, and the unique code numbers assigned to the investigational medicinal product and trial subjects.

Proprietary confidential information © 2022 Boehringer Ingelheim International GmbH or one or more of its affiliated companies

The investigator or designee will maintain records that document adequately that the subjects were provided the doses specified by the CTP and reconcile all investigational medicinal products received from the sponsor. At the time of disposal of remaining trial medication, the investigator or designee must verify that no remaining supplies are in the investigator's possession.

All unused medication will be disposed of locally by the trial site upon written authorisation of the Clinical Trial Leader. Receipt, usage and disposal of trial medication must be documented on the appropriate forms. Account must be given for any discrepancies.

4.2 OTHER TREATMENTS, EMERGENCY PROCEDURES, RESTRICTIONS

4.2.1 Other treatments and emergency procedures

There are no special emergency procedures to be followed. No additional treatment is planned. However, if adverse events require treatment, the investigator can authorise symptomatic therapy. In those cases, subjects will be treated as necessary and, if required, kept under supervision at the trial site or transferred to a hospital until all results of medical evaluations are acceptable.

4.2.2 Restrictions

4.2.2.1 Restrictions regarding concomitant treatment

In principle, no concomitant therapy is allowed except for hormonal contraceptives, hormonal replacement therapy, and SARS-CoV2 vaccination. All concomitant or rescue therapies will be recorded (including time of intake on trial days) on the appropriate pages of the CRF.

4.2.2.2 Restrictions on diet and life style

While admitted to the trial site, the subjects will be instructed not to consume any foods or drinks other than those provided by the staff. Standardised meals will be served at the times indicated in the [Flow Chart](#). No food is allowed for at least 4 h after drug intake.

From 1 h before drug intake until lunch, fluid intake is restricted to the milk served with breakfast (see Table [4.1.4: 2](#)), the water administered with the drug, and an additional 240 mL of water at 2 h and 4 h post-dose (mandatory for all subjects). From lunch until 24 h post-dose, total fluid intake is restricted to 3000 mL.

Alcoholic beverages, grapefruits, Seville oranges (sour or bitter oranges) and their juices, and dietary supplements and products containing St. John's wort (*Hypericum perforatum*) are not permitted from 7 days before the first administration of trial medication until after the last PK sample of each trial period is collected.

Poppy-seeds containing foods should not be consumed within 3 days before each admission to trial site, in order to avoid false-positive results in the drug screen.

Proprietary confidential information © 2022 Boehringer Ingelheim International GmbH or one or more of its affiliated companies

Methylxanthine-containing drinks or foods (such as coffee, tea, cola, energy drinks, or chocolate) are not allowed from 24 h before until 24 h after each administration of trial medication.

Smoking is not allowed during in-house confinement.

Excessive physical activity (such as competitive sport) should be avoided from 7 days before the first administration of trial medication until the end of trial examination.

Direct exposure to the sun or exposure to solarium radiation should be avoided during the entire trial.

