			4:00	12:00	240 mL fluid intake, thereafter lunch ³		X			X		X
			5:00	13:00			X					
			6:00	14:00			X					
			7:00	15:00			X					
			8:00	16:00			X			X		
			10:00	18:00	Dinner ³		X					
			12:00	20:00			X					X
		2	24:00	08:00	Breakfast (voluntary) ³ , discharge from trial site	X ^B	X			X	X	X
			34:00	18:00	Ambulatory visit		X			X		X
		3	48:00	08:00	Ambulatory visit		X					X
		4	72:00	08:00	Ambulatory visit		X					X
		5	96:00	08:00	Ambulatory visit		X					X
		6	120:00	08:00	Ambulatory visit		X					X
		7	144:00	08:00	Ambulatory visit		X					X
		11	240:00	08:00	Ambulatory visit	X ^B	X					X
		14	312:00	08:00	Ambulatory visit		X					X
FU	6	18 to 25			End of study (EoS) examination ⁴	X ^C		X	X	X	X	X

1. Subject must be informed and written informed consent obtained prior to starting any screening procedures. Screening procedures include physical examination, check of vital signs, ECG, safety laboratory (including drug screening and pregnancy test in female subjects), demographics (including determination of body height and weight, smoking status, alcohol history and suicidality assessment), relevant medical history, concomitant therapy and review of inclusion/exclusion criteria. Pharmacogenetic samples will be collected if needed.
2. The time is approximate; the procedure is to be performed and completed within the 3 h prior to drug administration.
3. If several actions are indicated at the same time, the intake of meals will be the last action.
4. At the end of study (synonym for end of trial), the EoS examination includes physical examination, vital signs, ECG, safety laboratory (including pregnancy test in women), recording of AEs, concomitant therapies and suicidality assessment.
5. Only urine drug screening and alcohol breath test as well as pregnancy test in women will be done at this time.
6. AEs and concomitant therapies will be recorded throughout the trial, but will be specifically asked for at the times indicated in the Flow Chart above.
7. Only for T_{fed} and R_{fed}

Proprietary confidential information © 2022 Boehringer Ingelheim International GmbH or one or more of its affiliated companies

8. Suicidality assessment using the Columbia-Suicidal Severity Rating Scale (C-SSRS): 'Screening/Baseline' version at Visit 1, and 'since last visit' version at visit 2-6.
9. Letter A, B and C define different sets of safety laboratory examinations (see Section [5.2.3](#)).

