4.3 TREATMENT COMPLIANCE

Compliance will be assured by administration of all trial medication in the trial centre under supervision of the investigating physician or a designee. The measured plasma concentrations of trial medication will provide additional confirmation of compliance.

Subjects who are non-compliant (for instance, who do not appear for scheduled visits or violate trial restrictions) may be removed from the trial and the CRF will be completed accordingly (for further procedures, please see Section [3.3.4.1](#)).

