Urinalysis (Stix)	Urine Nitrite (qual) Urine Protein (qual) Urine Glucose (qual) Urine Ketone (qual) Urobilinogen (qual) Urine Bilirubin (qual) Urine RBC/Erythrocytes (qual) Urine WBC/Leucocytes (qual) Urine pH	X X X X X X X X	-- -- -- -- -- -- -- --	X X X X X X X X
Urine sediment (microscopic examination if erythrocytes, leukocytes nitrite or protein are abnormal in urine)	Only positive findings will be reported (for instance, the presence of sediment bacteria, casts in sediment, squamous epithelial cells, erythrocytes, leukocytes)			

A: parameters to be determined at Visit 1 (screening examination)

B: parameters to be determined at Visit 2, 3, 4 and 5 (for time points refer to [Flow Chart](#))

C: parameters to be determined at Visit 6 (end of trial examination)

The tests listed in Table [5.2.3: 2](#) are exclusionary laboratory tests that may be repeated as required. The results will not be entered in the CRF/database and will not be reported in the CTR. Except for pregnancy tests and drug screening, it is planned to perform these tests during screening only. Pregnancy testing in women will be performed at screening, prior to each treatment period, and as part of the end of trial examination. Drug screening will be performed at screening and prior to each treatment period.

Table 5.2.3: 2 Exclusionary laboratory tests

Functional lab group	Test name
Drug screening (urine)	Amphetamine/MDA Barbiturates Benzodiazepine Cannabis Cocaine Methadone Methamphetamines/MDMA/Ecstasy Opiates Phencyclidine Tricyclic antidepressants
Infectious serology (blood)	Hepatitis B surface antigen (qualitative) Hepatitis B core antibody (qualitative) Hepatitis C antibodies (qualitative) HIV-1 and HIV-2 antibody (qualitative)
Pregnancy test (urine)	Beta human chorionic gonadotropin (beta-HCG)

To encourage compliance with alcohol restrictions, a breath alcohol test (e.g. AlcoTrue® M, [REDACTED]) will be performed prior to each treatment period, and may be repeated at any time during the trial at the discretion of an investigator or designee. The results will not be included in the CTR.

The laboratory tests listed in Tables 5.2.3: 1 and 5.2.3: 2 will be performed at [REDACTED], with the exception of drug screening and pregnancy tests. These tests will be performed at the trial site using M-10/14-PDT Surestep Multiline test and HCG-K20 test, respectively, or comparable test systems.

Laboratory data will be transmitted electronically from the laboratory to the trial site.

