6. INVESTIGATIONAL PLAN

6.1 VISIT SCHEDULE

Exact times of measurements outside the permitted time windows will be documented. The acceptable time windows for screening and the end of trial examination are provided in the [Flow Chart](#).

Study measurements and assessments scheduled to occur 'before' trial medication administration on Day 1 are to be performed and completed within a 3 h-period prior to the trial drug administration.

Up to 48 h after drug administration (planned time), the acceptable deviation from the scheduled time for adverse event/concomitant medication questioning, suicidality assessment, vital signs, ECG, and laboratory tests will be \pm 30 min, if not stated otherwise in the Flow Chart,

For PK sampling, no time window is defined for this period (i.e. up to 48 h after drug administration).

Starting from planned time of 48 hours after drug administration (and beyond) a time window of \pm 120 minutes will be allowed for all procedures

Starting from a planned time of 168 hours after drug administration (and beyond) a time window of \pm 26 hours will be allowed for all procedures

If scheduled in the Flow Chart at the same time as a meal, blood sampling, vital signs, and 12-lead ECG recordings have to be done first. Furthermore, if several measurements including venipuncture are scheduled for the same time, venipuncture should be the last of the measurements due to its inconvenience to the subject and possible influence on physiological parameters.

For planned blood sampling times, refer to the Flow Chart. While these nominal times should be adhered to as closely as possible, the actual sampling times will be recorded and used for the determination of pharmacokinetic parameters.

If a subject misses an appointment, it will be rescheduled if possible. The relevance of measurements outside the permitted time windows will be assessed no later than at the Report Planning Meeting.

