6.2.2 Treatment period

Each subject is expected to participate in 4 treatment periods (each consisting of Days -1, 1-7, 11 and 14 in each period). At least 17 days will separate drug administrations in the first, second, third and fourth treatment period.

In the evening of Day -1 of each treatment period, trial participants will be admitted to the trial site and kept under close medical surveillance for at least 24 hours following drug administration. The subjects will then be allowed to leave the trial site after formal assessment and confirmation of their fitness. On all other trial days, subjects will be treated in an ambulatory fashion.

For details on time points and procedures for collection of plasma samples for PK analysis, refer to [Flow Chart](#) and Section [5.3.2](#).

The safety measurements performed during the treatment period are specified in Section [5.2](#) of this protocol and in the Flow Chart. AEs and concomitant therapy will be assessed continuously from obtaining subject's written informed consent until the end of trial examination. For details on times of all other trial procedures, refer to the Flow Chart.

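### Does the ban on alcohol, grapefruit, Seville orange and St. John's wort lapse between one period's last PK sample and the next dose?

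*Protocol*

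**What the plan says.** Protocol section 4.2.2.2 prohibits alcohol, grapefruit, Seville orange and their juices, and products with St. John's wort "from 7 days before the first administration of trial medication until after the last PK sample of each trial period is collected".

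Two other rules in that section are worded differently. Excessive physical activity "should be avoided from 7 days before the first administration of trial medication until the end of trial examination", which gives one start and one end. Methylxanthine-containing food and drink "are not allowed from 24 h before until 24 h after each administration of trial medication", which ties both limits to every dose.

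The timing comes from three places:

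- Section 6.2.2: "At least 17 days will separate drug administrations in the first, second, third and fourth treatment period". No maximum is given.
- Flow Chart: the last PK sample of each period is planned at 312 h (Day 14), and admission is about 12 h before dosing.
- Section 6.1: "Starting from a planned time of 168 hours after drug administration (and beyond) a time window of" ±26 hours.

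On checks and consequences, section 5.2.3 schedules a test before each treatment period: "To encourage compliance with alcohol restrictions, a breath alcohol test". Flow Chart footnote 5 places it at admission: "Only urine drug screening and alcohol breath test as well as pregnancy test in women will be done at this time". Section 4.3 adds: "Subjects who are non-compliant (for instance, who do not appear for scheduled visits or violate trial restrictions) may be removed from the trial".

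**The concern.** The start of the ban is a single event, while its end recurs with each of the four periods. Read literally, the ban could stop after the period 1 sample, and nothing says when it would begin again. Only dose 1 is then expressly given seven days free of these items.

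Two things would be at stake. The first is conduct: the site and the trial team need to know whether a glass of wine or grapefruit juice on, say, Day 16 breaks a trial restriction, since a breach may lead to removal and must be assessed as a protocol deviation (SAP section 6.2). The second is precision: all four comparisons are within-subject across periods, and the 90% confidence intervals rest on the residual error of the ANOVA. Sporadic intake before doses 2 to 4 could add to that error if these items alter exposure.

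**Working it through.** **Inputs.** Minimum dose separation 17 days (Protocol 6.2.2). Last planned PK sample 312 h = 13 days (Flow Chart). Sampling window ±26 h from 168 h onward (Protocol 6.1). Lead before the first dose 7 days = 168 h (Protocol 4.2.2.2). Admission about 12 h before dosing (Flow Chart). The plan states no figure for this interval, so there is none to reproduce.

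**Step 1: the interval in doubt.** Interval = 24W − 312 h, with W the dose separation in days.

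- W = 17: 408 − 312 = 96 h.
- Sample taken 26 h late: 408 − 338 = 70 h. Sample taken 26 h early: 408 − 286 = 122 h.
- Less about 12 h in-house, when only food and drink from the staff are allowed: 84 h (58 to 110 h) as an outpatient.

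This occurs three times per subject. The roughly 13 days from each dose to its last sample are not in doubt on any reading in Step 2.

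**Step 2: what each reading implies.**

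| Reading | At W = 17 | General gap (planned sample time) |
|---|---|---|
| One continuous ban until every period's last sample has been collected | No gap | 0 |
| A 7-day lead before every dose | Lead starts at 408 − 168 = 240 h, before the 312 h sample (and before 286 h): no gap | 0 up to W = 20, since 312 + 168 = 480 h; then W − 20 days |
| Ban ends at each last sample and resumes at the next dosing | 96 h | W − 13 days |

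The third reading is the only one with a gap at 17 days, and it requires a restart at dosing that no sentence supplies. Without that restart, a ban that truly ended after period 1 would have nothing left to end in periods 2 to 4, and the reference to each period would be empty. The continuous reading gives every word a function: the ban begins once and holds until the last sample has been taken in each of the four periods. On either of the first two readings, every dose has at least the 7-day lead given to dose 1. Where they differ (W above 20), the extra free days fall before that lead begins.

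**Step 3: context.** A breath test meant to encourage compliance with alcohol restrictions, done before each treatment period, presupposes that such a restriction already applies. This supports the first two readings for alcohol. It does not speak to grapefruit, Seville orange or St. John's wort. The general rule against concomitant therapy (Protocol 4.2.2.1) may reach St. John's wort products.

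**Step 4: the analysis.** The model (Protocol 7.2.2, SAP 7.4.1) has sequence, subject within sequence, period and treatment effects. If intake before dosing were uniformly lower in period 1, the difference would go into the fitted period effect and leave the treatment contrasts alone. Only irregular intake would reach the residual error. For that to widen an interval, four things must all happen: the site adopts the third reading, subjects consume the items in those days, the items alter exposure, and the effect lasts through dosing. The visible text establishes none of these, so no size can be computed.

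**The case for a change.** The case for a change is that the sentence is faulty on any reading. If one continuous ban is meant, the end should be the last sample of period 4. If a ban per period is meant, the start should recur. Neighbouring rules show that both forms can be drafted clearly. Since each treatment is a single dose, the first administration most naturally means dose 1 of the trial, which weakens the reading with a lead before every dose. No upper limit on the washout is stated, so on the gap reading the interval grows by a day for each added day. From W = 20 the previous period's ban, at the planned sample time, covers none of the 7 days before the next dose. The safeguards are partial, because nothing scheduled at admission would detect grapefruit or Seville orange. A correction would cost one sentence and the matching subject information.

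The mismatch of start and end stands, and nothing in the Protocol or SAP expressly resolves it. The consequence does not. The gap still depends on an unstated restart at dosing, and separations beyond 17 days are illustrations rather than planned values. Removal under section 4.3 is discretionary. Deviations relevant to PK are decided no later than the Report Planning Meeting (Protocol 7.2.1.2), so a doubtful case would be judged before the analysis.

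**Conclusion.** The wording of section 4.2.2.2 is untidy, but it does not call for a change to the plan. The interval not expressly addressed is 96 h before each of doses 2 to 4 at the minimum separation (70 to 122 h with the sampling window, 58 to 110 h of it as an outpatient). On the continuous reading, which fits the words best and which the breath test supports for alcohol, the gap is zero. A site that follows that reading obtains sound data for all four comparisons.

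This rests on two assumptions: that the site does not infer a restart at dosing that the text does not state, and that the subject information, which is not available here, does not instruct volunteers otherwise. The documents give no effect of these items on BI 1358894 exposure, so no effect on the geometric mean ratios or their 90% confidence intervals can be derived. Rewording would make explicit what a sensible reader already takes from the sentence. It would alter no endpoint, stated figure or analysis.
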